11.2 Statistical Methods for Primary and Secondary Endpoints

Descriptive summary statistics (e.g. means and standard deviations, or median with inter-quartile, as appropriate) will be used to summarize the primary and secondary endpoints by study treatment. The primary and secondary efficacy endpoints will also be analyzed using appropriate models.

The primary endpoint, change in the oxygenation index over time, will be compared between treatment conditions using a linear mixed-effects regression model. The model will be estimated using likelihood estimation which will allow the inclusion of all collected data, regardless of the number of assessments available for assessment. Terms in the model will include the two stratification variables, treatment condition (active or placebo), time of assessment, condition-by-time, recruitment site and a site-by-treatment interaction term. A test of the treatment condition will directly test the main research question. Covariates identified by preliminary analysis as potentially confounding due to baseline differences will be added to the model.

The data analysis plan for secondary efficacy and safety endpoints has been provided in the Statistical Analysis Plan.

The primary and secondary endpoints (including clinical and biological data) will be adjusted for COVID-19 infection as a cause of ARDS, which is adjudicated by the study physicians.

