The DSMB will review adverse outcomes and protocol compliance. A pre-specified interim review will occur after 60 subjects have been enrolled and received study product; enrollment will continue during DSMB review. All pre-specified clinically important events and unexpected serious adverse events including death during hospitalization up to 28 days after investigational product infusion will be reported to the DSMB on an ongoing basis; the study will be stopped for a safety evaluation by the DSMB if they have any concerns or if three subjects have pre-specified clinically important events or unexpected serious adverse events EXCEPT death since death will be common in this critically ill population due the nature of the underlying illness (e.g., ARDS). COVID-19 (coronavirus disease 2019), a disease caused by SARS-CoV-2, emerged in the United States in March 2020 and rapidly became a global pandemic. The vast majority of our enrolled patients were COVID-19 patients who developed ARDS. We have updated the Clinical Protocol (version 14) explicitly include clinical and biologic variables that are relevant to COVID-19 induced ARDS. This updated Statistical Analysis Plan is to reflect the revisions of the updated Clinical Protocol.

This study is financed through a grant from the Department of Defense (DoD), and California Institute for Regenerative Medicine (CIRM) for funding University of California Davis as an additional enrollment site. Both the DoD and NHLBI provided support for the production of MSCs at the University of Minnesota. This Phase 2b trial has been submitted to an Investigational New Drug (IND) amendment for a Phase 2b component study under IND 15331.

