10 SAMPLE SIZE DETERMINATION

The sample size for this trial will be 60 patients in the hMSCs arm and 60 patients in the placebo arm, for a total of 120 patients with a balanced randomization of patients with $\text{PaO}_2:\text{FiO}_2 < 150$ mmHg. This sample size was determined on the basis of feasibility.

Given the sample size of 60 per treatment condition, in this multisite, randomized trial using oxygenation index as the primary outcome and measures taken at 6 time points, it is estimated the study will have 80% power to detect a difference between conditions for an effect size as low as 0.43. Using the pilot data from Day 4, for example, this would translate to approximately a difference of 1.29 in the oxygenation index.

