12.6 Analysis for Primary Efficacy Endpoint

The primary endpoint is the changes in the oxygenation index from the baseline to the time-points at 6, 12, 18, 24, 30 and 36 hours after infusion of study product. The oxygenation index will only be calculated when the patient is still being ventilated with positive pressure. If patient is on pressure support, oxygenation index will be treated as missing because the mean airway pressure is not reliable.

Descriptive summary statistics (e.g. means and standard deviations, or median with inter-quartile, as appropriate) will be presented for the oxygenation index values, as well as the changes of oxygenation index from the baseline to each following timepoint by allocated group in modified ITT population.

The change of oxygenation index, by allocated treatment groups in modified ITT Population, will be compared using two linear mixed-effects regression models: unadjusted and adjusted model. Both models will be estimated using maximum likelihood estimation, which will allow the inclusion of all collected data, regardless of the number of assessments available for assessment. All models will include the stratification variables: $\text{PaO}_2/\text{FiO}_2$ ($< 150 \text{ mmHg}$ or $\geq 150 \text{ mmHg}$) and trauma status (trauma vs. non-trauma). Terms in the unadjusted linear mixed-effects regression model will include the two stratification variables, treatment condition (active or placebo), time of assessment (by hour), condition-by-time, recruitment site and a site-by-treatment interaction term. A test of the treatment condition will directly test the main research question. The adjusted linear mixed-effects regression model will include all the variables from the unadjusted model described above plus covariates identified by preliminary analysis as potentially confounding due to baseline differences ($p\text{-value} < 0.20$). The treatment effects may vary with ARDS severity ($\text{PaO}_2/\text{FiO}_2$) or by trauma status, thus the interaction terms will be also included. Both unadjusted and adjusted models will be presented with coefficient with 95% confidence intervals.

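### SAP 12.6 adds treatment-by-P/F and treatment-by-trauma interactions to the oxygenation-index analysis without defining the treatment contrast, so a default treatment coefficient is not the overall difference for which 80% power is stated

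*SAP*

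**What the plan says.** SAP 10 gives the power statement: "it is estimated the study will have 80% power to detect a difference between conditions for an effect size as low as 0.43", with 60 patients per arm and six post-baseline measures. Protocol 11.1 says the same. Neither shows a formula, a model or a within-patient correlation.

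SAP 12.6 describes two linear mixed models for the change in OI and names neither as primary.

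- **Unadjusted model.** The term list is the two stratification variables, treatment, time, condition-by-time, site and site-by-treatment. The statement that the treatment term answers the trial's question comes straight after this list.
- **Adjusted model.** This adds baseline covariates that differ between arms at p < 0.20. The next sentence allows for effects that differ by P/F severity "or by trauma status, thus the interaction terms will be also included".

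Both models are to be reported as coefficients with 95% confidence intervals. No coding, contrast or stratum weights are stated.

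Protocol 11.2 has a single model: "Terms in the model will include the two stratification variables, treatment condition (active or placebo), time of assessment, condition-by-time, recruitment site and a" site-by-treatment interaction, plus possible confounders. It has no treatment-by-P/F or treatment-by-trauma term.

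On the likely stratum sizes, SAP 3 says only this: "The vast majority of our enrolled patients were COVID-19 patients who developed ARDS". Neither document gives a trauma count or a P/F split.

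**The concern.** Once treatment interacts with P/F stratum and trauma, the model has no single treatment coefficient that means the overall arm difference. What the software prints depends on choices the SAP leaves open.

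- With reference coding, the coefficient is the effect in one P/F stratum of one trauma class.
- With equal-weight margins (the usual Type III or least-squares-means output), trauma patients carry half the weight however few they are.

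Both are legitimate quantities, but neither is the difference between conditions that SAP 10 describes, and both are estimated less precisely. If the choice is left to the analysis stage, coding decides which effect is reported. SAP 12.7.1 extends the approach in parallel to lung injury score, dead space, RALE score, later OI and ventilatory ratio.

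**Working it through.** **Inputs from the documents.** 60 per arm; effect size 0.43; 1.29 OI units, so the implied SD is 1.29/0.43 = 3.0; six measures (SAP 10). Two-sided 5% (SAP 12.5). 1:1 allocation (SAP 12.2).

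**Assumptions not in the documents.** Equal correlation r between measures; complete data; the same true effect in every stratum; P/F and trauma balanced by arm and independent of each other; no site or time interaction in steps 2 to 4. Trauma count 4-24 of 120 and P/F <150 share 40-70%, shown as ranges.

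**Step 1: the plan's own figure.** For one measure per patient the noncentrality is 0.43 × √(60/2) = 2.355, and power is Φ(2.355 − 1.960) = 65% (64.7% by exact t). The mean of six measures has its variance multiplied by (1 + 5r)/6. Power of 80% needs noncentrality 1.960 + 0.842 = 2.802, so (1 + 5r)/6 = (2.355/2.802)² = 0.706 and r = 0.65. Exact t gives r = 0.634. At r = 0.5 and 0.8 exact power is 86.4% and 72.5%. The 80% therefore fits an overall two-arm comparison averaged over time, if r is about 0.63. The steps below take that 80% as given.

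**Step 2: variance with both interactions.** Let p be the share in the chosen P/F stratum and q the trauma share. A treatment effect evaluated at weights p\* and q\* has its variance, relative to the main-effect test, multiplied by

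V = 1 + (p\* − p)²/[p(1 − p)] + (q\* − q)²/[q(1 − q)].

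Power is about Φ(2.802/√V − 1.960).

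- Equal weights: p\* = q\* = 0.5.
- Non-trauma reference cell: p\* = 1, q\* = 0, so V = 1/p + q/(1 − q).
- Observed shares: p\* = p, q\* = q, so V = 1.

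**Step 3: results with a 50:50 P/F split.**

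| Trauma patients of 120 | V, equal weight | Power, equal weight | V, non-trauma reference cell | Power, reference cell | Power, observed shares |
|---|---|---|---|---|---|
| 4 | 7.76 | 17% | 2.03 | 50% | 80% |
| 6 | 5.26 | 23% | 2.05 | 50% | 80% |
| 12 | 2.78 | 39% | 2.11 | 49% | 80% |
| 24 | 1.56 | 61% | 2.25 | 46% | 80% |

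Worked example, 4 trauma patients, equal weight: V = 1 + 0.4667²/(0.0333 × 0.9667) = 7.76, and 2.802/√7.76 = 1.006, so power is Φ(−0.954) = 17%.

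**Step 4: other P/F splits.** With a P/F <150 share of 40-70% and either stratum as reference, the reference stratum holds 30-70% of patients.

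- Best case: V = 1/0.70 + 4/116 = 1.46, power 64%.
- Worst case: V = 1/0.30 + 24/96 = 3.58, power 32%.
- With a trauma reference cell, V = 1/p + (1 − q)/q, and power is about 7-22% over the same ranges.
- If the treatment test is read as a joint 3-df test of treatment and both interactions, noncentrality 2.802² = 7.85 gives 64%.

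**Step 5: terms already in both documents.** With seven equal sites, a reference-site coefficient has noncentrality 2.802/√7 = 1.06, or 18% power. With linear time over hours 6 to 36 and a random intercept at r = 0.648, the hour-0 treatment coefficient has variance ratio [0.648 + 0.352 × (1/6 + 21²/630)]/[0.648 + 0.352/6] = 1.35, or 67% power. The same difficulty therefore arises before any P/F or trauma interaction is added.

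**The case against.** The best reply concerns placement. The unadjusted term list omits the two interactions, and the statement about the main question sits beside that list. If the interaction sentence covers only the adjusted model, the unadjusted test is untouched and agrees with Protocol 11.2 on these terms. That stands. But no model is named primary, so one of two reported analyses of the primary endpoint is still affected.

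Second, the percentages are conditional. Stratum shares, coding and correlation are all unstated. Complete data are assumed, although SAP 13.1 calls missing OI common. With 36 trauma patients the equal-weight test recovers to 66-73%, and with 60 of 120 trauma and a 50:50 P/F split it equals the observed-share contrast at 80%. An analyst who chose observed-share weights would lose nothing. All of this stands; a small trauma stratum is an inference from SAP 3, not a count.

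Third, going back to the Protocol 11.2 terms does not by itself restore 80%, as step 5 shows. This also stands, and the fix covers it.

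Fourth, SAP 10 says of the number enrolled: "This sample size was determined on the basis of feasibility". The power sentence therefore describes the design rather than driving it. That lowers the stakes but does not make the statement apply to a different contrast.

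A reader might infer that the trial's primary analysis has 17-64% power, or that an effect of the planned size would usually be missed. The documents support neither. That span joins two different tests under assumed shares, some scenarios give 61-64%, and the affected model may not be the primary one.

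**Conclusion.** The point holds as a gap in specification. SAP 12.6 adds two treatment interactions that Protocol 11.2 does not list, does not say clearly which model carries them, and does not define the treatment contrast. In any model that contains them, neither the default coefficient nor an equal-weight margin is the overall difference to which the 80% at 0.43 refers.

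The size of the loss is illustrative only. If r is about 0.63, data are complete, the effect is common to all strata and site and time interactions are ignored, power is about 17-61% (equal weight, 4-24 trauma patients, 50:50 P/F split) or 32-64% (non-trauma reference cell, P/F <150 share 40-70%). It stays at 80% with observed-share weights. The cause is the undefined contrast across all treatment interactions, of which these two are part. It should be settled before unblinding.

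**What to change.** In SAP 12.6:

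1. Name the primary model.
2. Keep P/F stratum and trauma in it as main effects only, as in Protocol 11.2, and move treatment-by-P/F and treatment-by-trauma to separate models labelled as effect modification. Alternatively, if the interactions stay, test treatment with a pre-specified contrast weighted by the observed stratum proportions.
3. Define that contrast over time and site as well (which hours are averaged, and how sites are weighted), because condition-by-time and site-by-treatment raise the same problem.

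In SAP 10, state that the 80% at 0.43 applies only to this overall contrast, and give the within-patient correlation it assumes.

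The cost is SAP wording before unblinding. No patients or data are added and no heterogeneity analysis is lost. SAP 1 records that the primary model was revised at the DSMB's request in version 2.0 but does not say which terms changed, so the sponsor should check whether these interactions came from that request before moving them.

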12.7 Analyses for Secondary Efficacy Endpoints

12.7.1 Respiratory Physiology Endpoints

The secondary endpoints, such as acute lung injury score, pulmonary dead space and RALE score, expanded oxygenation index up to 7 days and the reduction in ventilator ratios, will be analyzed by linear mix-effects regression models using the modified ITT population, in a fashion parallel to the analyses of the primary endpoint of oxygenation index. Incidence of barotrauma will be analyzed by mixed-effects logistic regression models using the modified ITT population. Counted measures, such as ventilator free days, will be analyzed using zero-inflated negative binomial models in a parallel fashion as well. Achieving pressure support and second infection endpoint will be analyzed using a logistic regression model.

The acute lung injury score (LIS), pulmonary dead space, chest radiograph assessment of pulmonary edema (RALE score) at days 0, 1, 2, 3 and 7 (5 timepoints) will be summarized in modified ITT population by allocated group.

The reduction in ventilatory ratio at 6, 12, 18, 24, 36 hours from the baseline will be summarized in modified ITT population by allocated group.

The incidence of barotrauma will be categorized as yes or not on days 1, 2, 3 and 7, and summarized by patient counts and percentages. Evidence of barotrauma includes the following:

- Pneumothorax
- Bronchopleural fistula
- Tracheobronchial fistula;
- Pneumomediastinum
- Subcutaneous emphysema
- Pneumoatocoele

Ventilator free-days by 7, 14 and 28 days will be calculated as described in *Section 8.7*. They will be summarized as median and interquartile range by allocated group, separately.

Duration of assisted ventilation over 28 days will be calculated among survivors by day 28. It will be summarized as median and interquartile range.

Achieving pressure support ventilation equal to 5 cm H₂O with positive end-expiratory pressure (PEEP) equal to 5 cm H₂O for 2 hours will be categorized as yes or not, and summarized by patient counts and percentages.

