7.2 Inclusion criteria

Patients with the presence of ARDS within 14 days of initial ICU admission. ARDS is defined by presenting the following Criteria 1-3 within a 24-hour time period and at the time of enrollment:

1. A need for positive pressure ventilation by an endotracheal or tracheal tube with a $\text{PaO}_2/\text{FiO}_2$ ratio $< 250 \text{ mmHg}$ with $\geq 5 \text{ cm H}_2\text{O}$ positive end-expiratory airway pressure (PEEP), as per the Berlin Criteria, and
2. Bilateral infiltrates consistent with pulmonary edema on frontal chest radiograph, or bilateral ground glass opacities on a chest CT scan, and
3. No clinical evidence of left atrial hypertension as the explanation for the bilateral pulmonary infiltrates.
4. If the cause of ARDS is trauma, additional inclusion criteria will include ONE of the following relevant risk factors for developing ARDS:
 - a. Hypotension (systolic blood pressure[SBP] $< 90 \text{ mmHg}$) in the field or in the first 24 h after injury, or
 - b. Transfusion of 3 units of blood products in the first 24 hours following injury, or
 - c. Meets the new Critical Administration Threshold (CAT) criteria with at least 3 units of blood in one hour, or

- d. Blunt or penetrating torso trauma, or
- e. Long bone fractures, or
- f. The highest level of institutional trauma activation

ARDS diagnostic criteria defined:

- “Acute onset” is defined as follows: the duration of the hypoxemia criterion (#1) and the chest radiograph criterion (#2) must both be present \leq 14 days of initial ICU admission at the time of enrollment.
- Infiltrates considered “consistent with pulmonary edema” include any patchy or diffuse opacities not fully explained by mass, atelectasis, or effusion or opacities known to be chronic (>14 days of initial ICU admission). The findings of vascular redistribution, indistinct vessels, and indistinct cardiac borders alone are not considered “consistent with pulmonary edema” and thus will not count as qualifying opacities for this study.
- If a patient meets #1 and #2 inclusion criteria but has an echocardiogram with LV ejection $<$ 40% that ordered by treating clinicians because of clinical suspicion of left heart failure, the patient will be excluded.

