9.7 Radiographic Assessment of Lung Edema (RALE) Score

Radiographic Assessment of Lung Edema (RALE) score (128) will be used to evaluate the extent and density of alveolar opacities on chest radiographs at baseline, and days 1, 2, 3 and 7. To determine the RALE score, each radiograph will be divided into quadrants, defined vertically by the vertebral column and horizontally by the first branch of the left main bronchus. Each quadrant will be assigned a consolidation score from 0 to 4 to quantify the extent of alveolar opacities, based on the percentage of the quadrant with opacification and a density score from 1 to 3 to quantify the overall density of alveolar opacities, unless the consolidation score for that quadrant is 0. The density score allows for more quantitative assessment of the density of opacification by quadrant (see **Appendix L**). We will obtain the de-identified chest x-ray graphs at baseline and on days 1, 2, 3, 7, and evaluate the RALE scores. We will concurrently systematically evaluate for and record evidence of barotrauma including pneumothorax, pneumomediastinum, subcutaneous emphysema, and the presence of tube thoracostomy on the same set of radiographs.

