Appendix I. Barotrauma

Evidence of barotrauma includes the following:

- Pneumothorax
- Bronchopleural fistula
- Tracheobronchial fistula
- Pneumomediastinum
- Subcutaneous emphysema
- Pneumoatocoele

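### SAP 12.7.1 does not define barotrauma as new since baseline, so findings already present before infusion can be counted as events, although the baseline film is read for them

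*SAP*

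**What the plan says.** Both documents list the incidence of barotrauma on days 1, 2, 3 and 7 as a secondary respiratory endpoint (Protocol 6.2.1, SAP 7.2.1). SAP 12.7.1 makes this operational in two sentences: "The incidence of barotrauma will be categorized as yes or not on days 1, 2, 3 and 7", and "Incidence of barotrauma will be analyzed by mixed-effects logistic regression models using the modified ITT population". It then lists six qualifying findings, the same six that Protocol Appendix I introduces with "Evidence of barotrauma includes the following".

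In the same SAP section, lung injury score, dead space and RALE score "at days 0, 1, 2, 3 and 7 (5 timepoints) will be summarized in modified ITT population by allocated group". Barotrauma has no day 0.

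Protocol 9.7 provides a baseline film: "We will obtain the de-identified chest x-ray graphs at baseline and on days 1, 2, 3, 7, and evaluate the RALE scores". At the same reading, staff are to "record evidence of barotrauma including pneumothorax, pneumomediastinum, subcutaneous emphysema, and the presence of tube thoracostomy on the same set of radiographs". Tube thoracostomy appears in that sentence but not in Appendix I or in the SAP list.

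**The concern.** Incidence means new occurrence. The stated rule records whether a finding is present on each of four days, which is prevalence. Nothing in it separates a pneumothorax that developed after infusion from one that was there before.

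Pre-existing findings are possible. Every patient is on positive pressure ventilation at entry. One qualifying risk factor for trauma patients is "Blunt or penetrating torso trauma, or". None of the 22 exclusion criteria names barotrauma or a chest tube.

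Treatment cannot affect a finding that came before it. Counting such findings adds the same background to both arms and pulls the relative effect toward no difference. If the arms happen to differ at baseline, the difference carries into the result in either direction. The reading that would prevent this is already planned.

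**Working it through.** **Step 1. Baseline anchoring of endpoints in the SAP.**

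| Endpoint | Anchor |
|---|---|
| Lung injury score, dead space, RALE (12.7.1) | Day 0 included |
| Ventilatory ratio (12.7.1) | Reduction from baseline |
| Non-pulmonary SOFA (12.7.3) | Change from baseline summarised |
| Infections (12.7.2), thromboembolic events (12.7.8) | After study product administration |
| Barotrauma (12.7.1) | None stated |

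Protocol 9.7 covers the baseline reading. The time-events schedule also appears to carry a pre-infusion barotrauma mark, but its columns are hard to align in the available text, so this point rests on 9.7.

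**Step 2. Does SAP 12.8 close the gap?** It adjusts outcomes for the stratification variables, baseline APACHE III and the baseline measure, subject to p < 0.20 between arms. Take 60 per arm (SAP 10) and an assumed 10% baseline prevalence, which is 6 patients per arm.

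- 6 v 6: no difference, so no adjustment. Dilution is untouched.
- 6 v 10: pooled proportion 16/120 = 0.133; standard error = sqrt(0.133 × 0.867 × 2/60) = 0.062; z = (4/60)/0.062 = 1.07; p is about 0.28, so no adjustment. This imbalance is 6.7 percentage points.
- The trigger is first reached at 6 v 11 by chi-square (p = 0.191) or 6 v 13 by Fisher's exact test (p = 0.132).

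Where it is triggered, a baseline barotrauma term would help the modelled odds ratio. The counts and percentages would still include the old findings.

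**Step 3. Illustrative size.** The plan states no barotrauma rate, effect or power, so there is no figure to reproduce. Assume new-event rates p of 5% and 10%, baseline prevalence b equal in both arms, and every baseline finding still visible at follow-up.

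Recorded rate = b + (1 − b) × p

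| b | Lower arm | Higher arm | Relative risk | Risk difference |
|---|---|---|---|---|
| 0% | 5.0% | 10.0% | 2.00 | 5.0 points |
| 5% | 9.75% | 14.5% | 1.49 | 4.75 points |
| 10% | 14.5% | 19.0% | 1.31 | 4.5 points |
| 15% | 19.25% | 23.5% | 1.22 | 4.25 points |

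If only new findings count, and patients positive at baseline have none, the rates at b = 10% are 0.9 × 5% = 4.5% and 0.9 × 10% = 9.0%. The relative risk stays at 2.0.

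**Step 4. A second set of assumptions.** Take new rates of 15% (placebo) and 5% (hMSC), with b = 10%. Recorded rates are 23.5% and 14.5%, and the odds ratio moves from 0.30 to 0.55. Pre-existing findings make up 0.10/0.235 = 43% of placebo events and 0.10/0.145 = 69% of hMSC events. Power at two-sided 5% is 24%, against 41% if only patients free of barotrauma at baseline are compared.

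**The case against.** The other side has several fair points.

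- **The SAP is silent rather than wrong.** The word incidence can be read as new onset, and a careful programmer might apply it that way. A reader might infer that pre-infusion findings will certainly be analysed as new events; the text does not establish that. What stands is that the written rule allows it and that two programmers could derive different endpoints.
- **Chest tubes.** A reader might infer that a tube in place at enrolment counts as an event. It does not under SAP 12.7.1 or Appendix I, whose six findings do not include it. Protocol 9.7 can be read either as listing the tube as evidence of barotrauma or as asking for it to be recorded as well. That is a wording conflict to reconcile, not a counting rule in the SAP.
- **SAP 12.8 and stratification.** Larger baseline imbalances would trigger adjustment, and trauma is a stratification factor. So it is too strong to say that any chance imbalance becomes an apparent treatment effect. Step 2 shows what remains.
- **Trauma.** Both documents say that the vast majority of enrolled patients had COVID-19, so trauma patients should not carry the argument.
- **Size.** The rates are assumed, and full persistence is the unfavourable case. On the risk-difference scale the loss is small (5.0 to 4.5 points at 10% prevalence). Even with no baseline barotrauma, the sampling standard deviation for 5% v 10% is sqrt((0.0475 + 0.09)/60) = 4.8 points. The endpoint is imprecise under either definition.
- **Importance.** SAP 12.5 treats secondary endpoints as supportive and exploratory.

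**Conclusion.** The gap is real and limited. The endpoint is called incidence, the baseline reading is collected, and the SAP does not use it to decide what counts as an event. Findings present before infusion can enter the counts, and SAP 12.8 does not remove them when the arms are balanced or modestly imbalanced.

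The main consequence is dilution of the relative effect. Under the 5% v 10% assumption, a relative risk of 2.0 falls to between 1.49 and 1.22 for baseline prevalence of 5% to 15%. This rests on assumed rates, equal prevalence in the arms and full persistence. If baseline findings resolve sooner the dilution is smaller, and with none at baseline it vanishes. The primary analysis of oxygenation index is unaffected.

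A reader might also infer that leaving out days 4 to 6 is a defect. The documents do not support that. Days 1, 2, 3 and 7 are prespecified in both, and films on other days are taken only when available. Using them would need extra reading and would tie detection to how often clinicians order films.

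**What to change.** In SAP 12.7.1:

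1. Define an event as an Appendix I finding on the day 1, 2, 3 or 7 film that was absent on the pre-infusion film. A finding at a new site or on a new side counts as new, so patients with baseline barotrauma can stay in the modified ITT population.
2. Report baseline barotrauma by arm with the other baseline characteristics.
3. State how a missing baseline film is handled, since Protocol Appendix A lists chest X-ray as when available. One option is to treat such patients as free of barotrauma in the main summary and repeat it without them.

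Reconcile Protocol 9.7 with Appendix I and SAP 12.7.1 on whether tube thoracostomy alone counts. Keep the prespecified days.

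The cost is SAP wording, a small change to the derivation and slightly fewer counted events. The reading must note site and side for the new-site rule to work. No films are needed beyond those already planned.
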